Appendix C. EORTC QLQC30 questionnaire (English version)

ENGLISH

EORTC QLQ-C30 (version 3)

Please fill in your initials:

Your birthdate (Day, Month, Year):

13. Have you lacked appetite?

14. Have you felt nauseated?

16. Have you been constipated?

15. Have you vomited?

We are interested in some things about you and your health. Please answer all of the questions yourself by circling the number that best applies to you. There are no "right" or "wrong" answers. The information that you provide will remain strictly confidential.

Too	Today's date (Day, Month, Year): 31							
		Not at All	A Little	Quite a Bit	Very Much			
1.	Do you have any trouble doing strenuous activities, like carrying a heavy shopping bag or a suitcase?	1	2	3	4			
2.	Do you have any trouble taking a long walk?	1	2	3	4			
3.	Do you have any trouble taking a short walk outside of the house?	1	2	3	4			
4.	Do you need to stay in bed or a chair during the day?	1	2	3	4			
5.	Do you need help with eating, dressing, washing yourself or using the toilet?	1	2	3	4			
Du	ring the past week:	Not at All	A Little	Quite a Bit	Very Much			
6.	Were you limited in doing either your work or other daily activities?	_						
	rece you make at doing class you would be out any activities.	1	2	3	4			
7.	Were you limited in pursuing your hobbies or other leisure time activities?	1	2	3	4			
7. 8.	Were you limited in pursuing your hobbies or other							
	Were you limited in pursuing your hobbies or other leisure time activities?	1	2	3	4			
8. 9.	Were you limited in pursuing your hobbies or other leisure time activities? Were you short of breath?	1	2	3	4			
8. 9. 10.	Were you limited in pursuing your hobbies or other leisure time activities? Were you short of breath? Have you had pain?	1 1 1	2 2 2	3 3	4 4			

Please go on to the next page

1

2

3

3

4

4

ENGLISH

During the past week:	Not at All	A Little	Quite a Bit	Very Much
17. Have you had diarrhea?	1	2	3	4
18. Were you tired?	1	2	3	4
19. Did pain interfere with your daily activities?	1	2	3	4
20. Have you had difficulty in concentrating on things, like reading a newspaper or watching television?	1	2	3	4
21. Did you feel tense?	1	2	3	4
22. Did you worry?	1	2	3	4
23. Did you feel irritable?	1	2	3	4
24. Did you feel depressed?	1	2	3	4
25. Have you had difficulty remembering things?	1	2	3	4
26. Has your physical condition or medical treatment interfered with your family life?	1	2	3	4
27. Has your physical condition or medical treatment interfered with your social activities?	1	2	3	4
28. Has your physical condition or medical treatment caused you financial difficulties?	1	2	3	4

For the following questions please circle the number between ${\bf 1}$ and ${\bf 7}$ that best applies to you

29.	How woul	ld you rate	your overa	ll health dur	ing the past	week?	
	1	2	3	4	5	6	7
Ver	y poor						Excellent
30.	How woul	ld you rate	your overa	ll quality of	life during t	he past wee	k?
	1	2	3	4	5	6	7
Ver	y poor						Excellent

© Copyright 1995 EORTC Quality of Life Group. All rights reserved. Version 3.0

Appendix D. EORTC ELD14 questionnaire (English version)

ENGLISH

EORTC QLQ-ELD14

Patients sometimes report that they have the following symptoms or problems. Please indicate the extent to which you have experienced these symptoms or problems during the past week. Please answer by circling the number that best applies to you.

During the past week:	Not at All	A Little	Quite a Bit	Very Much	
31. Have you had difficulty with steps or stairs?	1	2	3	4	
32. Have you had trouble with your joints (e.g. stiffness, pain)?	1	2	3	4	
33. Did you feel unsteady on your feet?	1	2	3	4	
34. Did you need help with household chores such as cleaning or shopping?	1	2	3	4	
35. Have you felt able to talk to your family about your illness?	1	2	3	4	
36. Have you worried about your family coping with your illness and treatment?	1	2	3	4	
37. Have you worried about the future of people who are important to you?	1	2	3	4	
38. Were you worried about your future health?	1	2	3	4	
39. Did you feel uncertain about the future?	1	2	3	4	
40. Have you worried about what might happen towards the end of your life?	1	2	3	4	
41. Have you had a positive outlook on life in the last week?	1	2	3	4	
42. Have you felt motivated to continue with your normal hobbies and activities?	1	2	3	4	
43. How much has your illness been a burden to you?	1	2	3	4	
44. How much has your treatment been a burden to you?	1	2	3	4	

[©] QLQ-ELD14 Copyright 2001 EORTC Quality of life Group. All rights reserved

Appendix E. EQ-5D-5L questionnaire (English version)

Health Questionnaire (EQ-5D-5L)

Under each heading, please tick the ONE box that best describes your health TODAY.

MO	BILITY
□ 1	I have no problems in walking about
2	I have slight problems in walking about
	I have moderate problems in walking about
4	I have severe problems in walking about
_ 5	I am unable to walk about
SEL	F-CARE
_1	I have no problems washing or dressing myself
_ 2	I have slight problems washing or dressing myself
3	I have moderate problems washing or dressing myself
4	I have severe problems washing or dressing myself
5	I am unable to wash or dress myself
USI	JAL ACTIVITIES (e.g. work, study, housework, family or leisure activities)
_ ₁	I have no problems doing my usual activities
2	I have slight problems doing my usual activities
3	I have moderate problems doing my usual activities
4	I have severe problems doing my usual activities
5	I am unable to do my usual activities
PAI	N / DISCOMFORT
□ 1	I have no pain or discomfort
2	I have slight pain or discomfort
3	I have moderate pain or discomfort
4	I have severe pain or discomfort
5	I have extreme pain or discomfort
AN)	KIETY / DEPRESSION
_ 1	I am not anxious or depressed
2	I am slightly anxious or depressed
3	I am moderately anxious or depressed
4	I am severely anxious or depressed
5	I am extremely anxious or depressed

[figure not shown]
UK (English) © 2009 EuroQol Group EQ-5D™ is a trade mark of the EuroQol Group

Health Questionnaire (EQ-5D-5L)

- · We would like to know how good or bad your health is TODAY.
- This scale is numbered from 0 to 100.
- 100 means the best health you can imagine.
 0 means the worst health you can imagine.
- Mark an X on the scale to indicate how your health is TODAY
- Now, please write the number you marked on the scale in the below.

YOUR HEALTH TODAY =

UK (English) © 2009 EuroQol Group EQ-5D™ is a trade mark of the EuroQol Group

Appendix F. Shortened version of the iMTA Medical Consumption Questionnaire

Questionnaire about your use of care

Researchers call this questionnaire the iMTA Medical Consumption Questionnaire (iMCQ).

July 2018 version, amended for IMPORTANT study

General questions

Question A1. On what date did you fill in this questionnaire?

Day	Month	Year	

Questions about healthcare use

Comment

We would like to know which doctors you have consulted in the past 3 months. It is about consultations for yourself. Other healthcare providers also count. For example, the physiotherapist.

Which consultations count?

- Control visits
- Appointments because you had a physical or psychological complaint
- Appointments where the doctor came to your home
- Telephone appointments
- Phone calls with the recipe line

Which consultations do not count?

- · Appointments for another person, for example for your husband or wife
- Telephone calls to make an appointment

Are you unsure about the exact number of consultations? Please fill in how many consultations you have had approximately.

Question 1. Have you consulted a general practitioner in the past 3 months	Question 1. Have	you consulted a	general	practitioner	in the	past 3 months
--	-------------------------	-----------------	---------	--------------	--------	---------------

] No] appointments
Question past 3 m	2. How many appointments did you have with a social worker in the onths?
	No appointment appointments
	3. How many appointments did you have with a physiotherapist in the onths? Add up all appointments with these therapists.
	No appointment appointments

IMPORTANT trial_ protocol version 4.0_18Nov2024_EN Page **59** of **62**

Question 4. How many appointments did you have with a psychologist, a psychotherapist or psychiatrist in the past 3 months? Add up all appointments with these healthcare providers.					
☐ No appointment☐ appointments					
Question 5a. Have you received home care in the past 3 months?					
☐ No ☐ Yes					
Have you ticked "Yes"? Then answer questions 5b through 5d. Otherwise, continue with question 6.					
Question 5b. What kind home care have you had in the past 3 months? You can tick more than 1 box.					
Housekeeping and domestic help example: vacuuming, making bed, going for daily groceries					
Personal care example: help with bathing or dressing					
Nursing example: putting on a bandage, administering medication, measuring blood pressure					
Question 5c. How many weeks did you have this home care? Count up all weeks in the past 3 months. Note: a period of 3 months counts 13 weeks .					
Domestic help: weeks in the past 3 months					
Personal care: weeks in the past 3 months					
Nursing: weeks in the past 3 months					

IMPORTANT trial_ protocol version 4.0_18Nov2024_EN Page **60** of **62**

Question 5d. How many hours of home care did you receive on average in these weeks?

Domestic I	nelp:	on average	hours a v	veek			
Personal c	are:	on average	hours a v	veek			
Nursing:		on average	hours a v	veek			
		received help r psychologica					ıce
	No Yes						
•	ticked "Yes"? , go to questic	Then answer qu on 8.	uestions 7b	through	7d.		
		d of help from nonths? You ca				ntances ha	ave
	Domestic hel example: vacu care of childre	ıuming, making b	oed, shoppir	ng, preparii	ng food ai	nd drinks, ta	aking
	Personal care example: help medicines	e with showering o	or dressing,	help with e	eating and	d drinking o	r giving

Question 6c. How many weeks did you have this home care? Count up all the weeks in the past 3 months. *Note: a period of 3 months counts as 13 weeks.*

Domestic help:	weeks in the past 3 months					
Personal care:	weeks in the past 3 months					
Practical help:	weeks in the past 3 months					
Question 6d. How many hours of home care did you receive on average in these weeks?						
Domestic help:	on average hours a week					
Personal care:	on average hours a week					
Practical help:	on average hours a week					
Question 7. Have you been admitted to a residential care centre or nursing home in the past 3 months? Have you been admitted more than 1 time in the past 3 months? Then add all the days together.						
☐ No ☐ Yes, for days in the p	past 3 months					

That was the last question.

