Healthcare costs: To estimate costs for medication, the prescription data (product, dosage, frequency) will be collected in the eCRF. Data on the utilization of concomitant medication will also be collected. Local medication list prices will be obtained with the help of consortium partners to complete the computation of medication costs. Hospital resource use will be collected in the eCRF. This includes the number of outpatient visits, admission and discharge dates of hospitalization, costs for disease monitoring (e.g., blood count, liver function, electrocardiogram), laboratory and imaging costs (e.g., CT, bone scan), and any treatment initiated to address adverse events (e.g., neutropenia). Data on non-hospital medical resource use will be reported by patients using a shorted version of the iMTA Medical Consumption Questionnaire (iMCQ; Appendix F). Healthcare resource use will be valued using reference prices where available, or prices in previously published literature when reference prices are not available.

Societal costs: To allow for an economic evaluation taking a societal perspective, relevant societal costs will be collected. Informal care utilization will be measured using a limited number of questions on volume and type of informal care used. The valuation of informal care will be done using local tariffs. Given the age of the target population of the trial, it is expected that the majority of patients are not performing paid labor. Therefore, productivity costs will not be measured.

Measurements: All questionnaires collecting patient reported data for the economic evaluation (i.e., the EQ-5D-5L, and the abbreviated iMCQ for non-hospital healthcare costs including questions on informal care use) will be completed every 3 months during the first 12 months and every 6 months thereafter until disease progression, participant / physician decision to stop, death, or up to 24 months whichever occurs first. In addition, the EQ-5D-5L will be completed at baseline.

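### Items 6c and 6d of the shortened iMCQ, the only informal-care volume items, repeat the block 5 home-care wording, so informal care may be misrecorded

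*Protocol*

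**What the plan says.** Section 23 (Cost-effectiveness analysis), under societal costs, states: "Informal care utilization will be measured using a limited number of questions on volume and type of informal care used". It adds: "The valuation of informal care will be done using local tariffs". Productivity costs are not measured, so informal care is the only societal cost that the section names. The questions are in the abbreviated iMCQ, reproduced in English in Appendix F.

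Block 5 of Appendix F opens with "Question 5a. Have you received home care in the past 3 months". After a question on the kind of care, it asks for volume: "Question 5c. How many weeks did you have this home care? Count up all weeks in the past 3 months" and "Question 5d. How many hours of home care did you receive on average in these weeks". The answer rows are domestic help, personal care and nursing.

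Block 6 turns to another source of help. Its first two stems (6a and 6b, numbered here by inference from 6c and 6d) are damaged in the available text. The legible parts ask whether the patient received help in connection with psychological or other problems, and what kind of help came from acquaintances. The volume items then read "How many weeks did you have this home care? Count up all the weeks in the past 3 months" (6c) and "Question 6d. How many hours of home care did you receive on average in these weeks" (6d). The rows are domestic help, personal care and "Practical help".

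**The concern.** The form uses home care as its name for the service in block 5. When 6c and 6d use the same name, a patient who reads them literally is asked again about block 5. A patient who has just answered No to 5a is sent on to question 6 and, after reporting help from acquaintances, is asked for weeks and hours of a service already denied. A patient who has both kinds of care may enter the block 5 figures a second time.

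Informal care carries the societal perspective alone, and cost-effectiveness is a listed secondary endpoint. The randomized cohort is vulnerable or frail and aged at least 70, so help from family or acquaintances, with or without home care, is plausible.

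The safeguards described would not catch a complete but misread answer. The questionnaire is self-completed, electronically or by post. Staff checking of replies with the patient is described for the geriatric assessment only, and paper forms are reviewed for completeness.

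**Working it through.** The protocol gives no figure to reproduce here, so the check sets the two blocks side by side.

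| Element | Block 5 | Block 6 |
|---|---|---|
| Subject set by the opening items | home care | help from acquaintances |
| Weeks item (c) | this home care | this home care; one article added |
| Hours item (d) | hours of home care | identical apart from the item number |
| Answer rows | domestic help, personal care, nursing | domestic help, personal care, practical help |
| Skip instruction | to 5b–5d, otherwise question 6: correct | to 7b–7d, otherwise question 8: these do not exist, as the items are numbered to 6d and the form ends at question 7 |

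The match at (c) and (d) is carried-over text. The faulty skip numbers in the same block are a second sign that it was not fully edited.

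**How the items enter the cost.** The natural volume formula, which the protocol does not state, is the sum over types of help of weeks (6c, at most 13 per recall period by the form's own note) × hours per week (6d). Write I for a patient's true informal hours and F for the home-care hours from block 5. Three readings are possible:

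1. The patient takes 6c and 6d to mean the help just reported. Recorded informal volume = I, which is correct.
2. The patient takes them to mean home care and has none. Recorded volume = 0 or missing.
3. The patient takes them to mean home care and has some. Recorded volume = F, and F is valued once in block 5 and again as informal care.

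**Illustration for one patient.** Only the 13 weeks come from Appendix F. The 8 hours per week of informal help and 3 hours per week of home care are assumed.

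- True informal volume: 13 × 8 = 104 hours.
- Reading 2: 0 recorded instead of 104, a loss of 100%.
- Reading 3: 13 × 3 = 39 recorded instead of 104. The shortfall is 104 − 39 = 65 hours, and 65/104 = 62.5%. The same 39 hours are also costed twice.

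**Effect on a comparison of arms.** Suppose a share p of patients misreads, equal in both arms and unrelated to hours. Let ΔI and ΔF be the true differences between arms in mean informal and home-care hours.

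- If all misreaders record zero, the recorded difference is (1 − p) × ΔI, which is shrunk toward zero.
- If all misreaders repeat block 5, it is (1 − p) × ΔI + p × ΔF, a mixture of two services.

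None of p, ΔI and ΔF is given in the protocol. For an individual patient the error runs from none to full loss or duplication; for the trial it cannot be quantified.

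**The case against.** The strongest reply is that context puts the patient right. The opening item of block 6 filters on help received, and the next asks what kind. The word this in 6c points back to the types just ticked, and 6d refers back to the weeks in 6c. The practical-help row does not occur in block 5, which has nursing instead. On this view, a patient who has just reported help from acquaintances is unlikely to enter zero weeks for it. Block 5 also never describes its home care as professional, so a patient may apply the term to help at home from anyone.

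This reply stands in part. A reader might infer from the wording that informal care is recorded as zero, or formal care counted twice, as a matter of course. The protocol does not support that: these are possible misreadings of unknown frequency, and correct answers are a third outcome. The cues do not remove the ambiguity, however. Item 6d lacks the pointing word, two of the three rows have the same labels in both blocks, and the skip text sends the patient to items that do not exist.

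It is also fair to say that the wording patients see is unknown. Section 22 provides for questionnaires in the local language across six countries, and only the English version is shown. The translations may or may not contain the slip.

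**Conclusion.** The wording error is real. The two items that alone quantify informal care name the service of the preceding block. Under-recording of informal care, or double counting of formal care, is possible, but its frequency and size cannot be derived from the protocol. The hours in the illustration are assumptions that show the mechanism only.

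A reader might go further and infer that the societal-perspective ICER is wrong. That does not follow. Both randomized arms receive the same form, only one component of incremental cost is exposed, and the bias depends on quantities that the protocol does not give. The healthcare-cost items themselves are unaffected, as are time to treatment failure, the clinical secondary endpoints, the sample size and the error rates.

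This is a minor point, worth correcting because it concerns a patient-completed item and hours missed at a three-month recall cannot be reliably recovered later. It rests on volume being computed as weeks × hours, and on block 6 being the informal-care block, which its legible text and section 23 support.

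**What to change.** Reword 6c to: *How many weeks did you have this help from family or acquaintances?* Reword 6d to: *How many hours of this help did you receive on average in these weeks?* The names for the helpers should match the opening items of block 6 in the source form. In the same edit, correct the block 6 skip text so that it points to 6b–6d and, otherwise, to question 7.

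Check whether the local-language and eCRF versions carry the same wording, and correct those that do. Record the form version with each response. In data already collected, review records where the 6c and 6d entries equal those of 5c and 5d, and records where help was reported in 6a but weeks are zero or blank.

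The cost is a minor revision of Appendix F, its translations and one eCRF form. The downside is a change of wording part-way through data collection, which the version flag lets the health-economic analysis take into account.

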- -All study-related information will be collected from academic Hospitals through patient journal with help with the National Patient Overview (a national electronic platform that connects the electronic patient records from different Hospitals in Sweden).

14. Decentralized approach

The trial enables a hybrid decentralized approach where the initial patient visit should be in-person whereas the visits for efficacy and toxicity evaluation can be performed digitally according to local practices.

The study protocol suggests that the following patient visits can be performed digitally: efficacy evaluation during treatment phase after agreement between the treating physician and the patient; toxicity evaluation before each cycle.

All PROMs will primarily be collected electronically through the eCRF system supporting the decentralized approach of the trial. The eCRF system will collect all PROMs but the calculations and interpretations of scores from each questionnaire will be performed by the investigators. If patients do not have access to electronical means, questionnaires will be sent to the patients per post thus allowing data collection without the need for the patient to be at the Hospital in person.

The digital patient visits for efficacy and/or toxicity assessment will be performed using the digital solution that is locally approved.

15. Interim analysis and design adaptations

A toxicity-driven interim analysis will be performed when 100 patients will be included to the study to evaluate the toxicity rates and assess the need for adaptations in terms of initial dose adjustment strategies for vulnerable/frail patient cohort.

The Independent Data Monitoring Committee (IDMC), consisting of three independent clinical experts in oncology and geriatrics, is responsible for providing external oversight of patient safety in IMPORTANT trial independently of the Clinical Trial Committee. After reviewing the aggregated toxicity data, IDMC may recommend the trial continue without modifications, continue with specific modifications, or be stopped for safety concerns. There will be no prespecified rules for stopping the trial due to safety concerns. The recommendations of the IDMC will be communicated to the Clinical Trial Committee.

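### Appendix F: the skip instruction after the informal-care question is numbered one too high, so nursing-home days and informal-care detail may be missed

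*Protocol*

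**What the plan says.** Protocol Section 23 (Cost-effectiveness analysis) makes the form in Appendix F a data source for the economic evaluation: "Data on non-hospital medical resource use will be reported by patients using a shorted version of the iMTA Medical Consumption Questionnaire". The same section uses it for informal care, which feeds the societal perspective. Table 1 in Section 12 schedules it at months 3, 6, 9, 12, 18 and 24, until progression, a decision to stop, or death.

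In Appendix F the filter on professional home care (5a) sends Yes to 5b through 5d and then says "Otherwise, continue with question 6". The next filter asks about help from family or acquaintances. Its routing line is broken in the text at hand (one fragment reads "Then answer qu on 8"), but the targets 7b, 7d and 8 are legible. The items that follow are printed as "Question 6c. How many weeks did you have this home care" and a matching 6d. Then comes "Question 7. Have you been admitted to a residential care centre or nursing home in the past 3 months", and the form closes with "That was the last question".

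On how the form is given, Section 14 says "All PROMs will primarily be collected electronically through the eCRF system supporting the decentralized approach of the trial", with postal forms for patients who lack electronic access. Section 22 says that questionnaires are given in the local language, and that paper forms are to be reviewed for completeness and patients encouraged to fill gaps.

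**The concern.** The routing line does not match the numbering of the form it stands in. A patient without informal care who obeys it never reaches the question on residential or nursing-home stays. A patient with informal care is pointed to items that are not there, and may pass over the type, weeks and hours of help.

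Both matter for the economic evaluation. The randomized cohort is vulnerable or frail and aged at least 70, a group in which institutional care and family help are relevant cost items. The answers cannot be recovered later: a statistical analysis plan can say how to handle a blank, but it cannot supply an answer the form steered the patient away from.

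The pattern of loss is also awkward. Question 7 would go missing according to the informal-care answer. If every patient obeyed the instruction, there would be no Question 7 answers at all among forms with informal care No, and any imputation would have to borrow from forms with informal care Yes on an assumption that the data could not test.

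**Working it through.** No sample size, power or event count is involved, so there is no figure to reproduce. The check traces the numbering and the skip instructions of Appendix F in order.

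| Filter | Answer | Printed target | What the form contains | Match |
|---|---|---|---|---|
| 5a, home care | Yes | 5b–5d | 5b, 5c, 5d | yes |
| 5a, home care | No | 6 | the informal-care block | yes |
| Informal care | Yes | 7b–7d | block numbered 6 (6c and 6d legible) | no |
| Informal care | No | 8 | Question 7, then the end of the form | no |

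**Is this an artefact of reading the PDF?** The routing line is scrambled, and the labels of the first two informal-care items are not legible. The block number follows from two places that are legible: 5a sends No answers to question 6, and the later items are 6c and 6d. The targets 7b, 7d and 8 are each one higher than the numbering requires (6b, 6d and 7). Broken extraction can reorder or drop characters, but it would not raise three numbers by one. The No branch does not depend on the illegible labels at all: Question 7 and the closing line are both clear, so there is no question 8.

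**Is there another source for nursing-home days?** The hospital resource use that Section 23 assigns to the eCRF comprises outpatient visits, hospital admission and discharge dates, monitoring, laboratory tests, imaging and treatment of adverse events. Residential or nursing-home days are not among them. Question 7 is therefore the only source that the protocol names.

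**How often can it recur?** Table 1 gives months 3, 6, 9, 12, 18 and 24, which is six administrations for a patient who stays in the treatment phase for 24 months, and fewer for the others.

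**Has it been corrected?** The appendix carries the version 4.0 footer, and the change history in Section 38 lists no correction to this form.

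**How large is the loss?** The share of forms with Question 7 missing for this reason is

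share lost = (share answering No to informal care) × (share of forms carrying the wrong routing) × (share of those patients who obey it and are not caught by a completeness check).

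The protocol gives none of the three factors, so no estimate is possible.

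**The case against.** The strongest reply is that the slip may never have reached many patients, and that there are safeguards where it did.

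- **The form shown may not be the form used.** Appendix F is the English text. The sites are in Sweden, Finland, Norway, Italy, Spain and Greece, questionnaires are given in the local language, and collection is mainly electronic. Neither the electronic routing nor any translation is shown. This stands: it makes the reach unknown, though it does not make the printed form right.
- **Paper forms are checked.** The completeness review in Section 22 should find a blank Question 7. This stands in part. It may work less well for forms sent by post, and a reviewer who trusts the printed skip may accept the blank as intended.
- **The instruction cannot be obeyed in full.** A patient who looks for question 8 finds Question 7 as the last item, and some will answer it. Likewise, a patient who answers Yes has the right follow-up items directly below. This stands.
- **The reach is narrow.** Cost-effectiveness is a secondary endpoint and is not one of the two that Section 22 names as key (overall treatment utility and overall survival). This stands.

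A reader might infer more than the documents support:

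- *That every form with informal care No loses Question 7.* If 40–70% of forms carried a No, an assumed range with no basis in the protocol, then 40–70% would be lost only if all forms carried the error, all patients obeyed it and no check caught it. That is a ceiling, not an estimate.
- *That skipped items will pass for no admission.* Question 7 has its own No box, so a blank can be told apart from a ticked No. It becomes zero only if the analysis makes it so, and the protocol does not say that it will; Section 23 leaves the full analysis to the statistical analysis plan.
- *That the comparison of costs between arms is biased.* The printed routing is the same in both arms. Distortion of the incremental cost would need starting dose to affect admissions or informal care, and the documents offer no evidence on that. That people in institutions tend to answer No to informal care is plausible but is also not shown.

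**Conclusion.** The error is real and stands in the current version of the form: the pointers after the informal-care filter are one too high, and their targets do not match the form. Followed as printed, the No branch bypasses the only source the protocol names for residential or nursing-home days, and the Yes branch misdirects patients away from the informal-care detail. These data may be missed, at up to six administrations per patient. How many will be missed cannot be judged from the protocol, because that depends on the electronic form, the translations, the completeness checks and patients' behaviour. The effect is confined to the cost-effectiveness endpoint; the primary endpoint, the sample size and the safety analysis are untouched. The point should be corrected because the correction is simple and answers not collected cannot be restored. The conclusion rests on reading the broken line as pointing to 7b through 7d and to question 8, which the legible fragments support.

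**What to change.** 1. In Appendix F, change the routing after the informal-care filter so that Yes leads to 6b through 6d and No leads to question 7.
2. Verify the same routing in the eCRF build and in every translated version, electronic and paper, and record which of them carried the error and over which dates.
3. For forms already completed with informal care No and Question 7 blank, treat residential or nursing-home days as missing, not as zero, and state this in the analysis plan for the economic evaluation.

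The cost is one corrected questionnaire page with its translations and a routing check in the eCRF. No extra visits or assessments are needed.
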